I herewith declare that I agree with the protocol described in detail in this document and agree to conduct the study in accordance with the protocol and in compliance with Good Clinical Practice and all applicable regulatory requirements.

Accepted by

Principal Investigator Signature	Printed name	Date

Protocol Synopsis

Sponsor:	Levita Magnetics
Protocol Title:	Prospective, multi-center, single-arm, open label study designed to assess the safety and feasibility of the use of the Dual Robotic Arm Accessory with the Levita Magnetic Surgical System in laparoscopic procedures
Protocol Number:	CP008
Investigational Device:	Levita Dual Robotic Arm Accessory (DRAA)
Device Description:	The Dual Robotic Arm Accessory (DRAA) for the MSS comprises two collaborative robotic arms, which along with their controllers and control software, are intended for use in medical applications, and additional adaptors, for 1) attaching the Magnetic Controller of the commercially available Levita Magnetics MSS to one robotic arm and 2) attaching a commercially available camera and endoscope to the second robotic arm. The design of the robotic arms, referred to as the Scope Arm and the Magnet Arm, includes several redundant safety features that make them well suited for use with the MSS in the operating
	room environment, including hardware and software safety controls.
	When mounted on the Scope Arm, an endoscope can be pivoted and translated as controlled by the user, while maintaining minimal motion at the point where the endoscope enters the patient's body via a standard trocar. Similarly, when mounted on the Magnet Arm, the Magnetic Controller can be moved to different positions on or away from the abdominal wall.
Study Objective:	The purpose of this study is to evaluate the safety and feasibility of the Dual Robotic Arm Accessory (DRAA) used with the Levita Magnetic Surgical System (MSS).
Study Design:	Prospective, multi-center, single-arm, open label study.
Enrollment Size and Number of Sites:	Up to 50 subjects will be competitively enrolled in up to 3 clinical sites in Chile.

CP008 Revision: A Date: 13Sep2022	CONFIDENTIAL	Page 6 of 41
This document contains proprietary and confidential information of Levita Magnetics.		
Do not copy, distribute, or sha	re with others without prior written authoriza	ation from Levita Magnetics.

Subject Population:	All patients at least 18 years of age presenting for elective laparoscopic surgery are potential candidates.
Rationale:	Levita has developed a Robotic Platform (DRAA) to assist in external management of the controlling magnet and the laparoscopic camera, which would give better control of surgical tools to the surgeon. The DRAA replaces the commercially available surgical support arm that is currently used with the MSS.
Safety Outcomes:	All adverse events will be captured and reported. Adverse events will be summarized by relatedness to the device and/or procedure, seriousness and level of severity. If device related, AEs will be further characterized as to relationship to the MSS the DRAA or both.
Feasibility Outcomes:	 Ability to utilize the Levita MSS with the DRAA as intended in laparoscopic procedures. The following outcomes will be considered in this feasibility study: The DRAA is able to engage, move, and decouple with the MSS as intended / controlled by the surgeon The DRAA is able to provide adequate endoscopic visualization via a conventional endoscopic system as intended / controlled by the surgeon The procedure is successfully performed with the MSS and DRAA. The MSS or the DRAA cannot be successfully used and due to a MSS or DRAA performance issue the procedure must be converted to an open procedure.
Inclusion Criteria:	Participants must meet ALL of the following inclusion criteria to be eligible for participation in the study: At least 18 years of age Scheduled to undergo elective laparoscopic procedure Willing and able to provide a written Informed Consent Form (ICF) to participate in the study prior to any study required procedures
Exclusion Criteria:	Individuals must be EXCLUDED from participation in this study if ANY of the following exclusion criteria are met: Individuals with pacemakers, defibrillators, or other electromedical implants Individuals with ferromagnetic implants Significant comorbidities: cardiovascular, neuromuscular, chronic obstructive pulmonary disease, and urological disease (renal failure)

CP008 Revision: A Date: 13Sep2022	CONFIDENTIAL	Page 7 of 41
This document contains proprietary and confidential information of Levita Magnetics.		of Levita Magnetics.

	Clinical history of impaired coagulation confirmed by abnormal blood tests Anatomical abnormality or disease of intended target tissue noted after initiation of index procedure that would prevent device use Pregnant or wishes to become pregnant during the length of study participation Individual is not likely to comply with the follow-up evaluation schedule Participating in a clinical trial of another investigational drug or device Prisoner or under incarceration
Study Duration / Follow-up Period	Subjects will be followed for 30 days post-procedure, with follow-up visits at hospital discharge, 7 days, and 30 days post-procedure.
Clinical Sites and Site Principal Investigators*:	[name] Hospital Luis Tisne Santiago, Chile [name] Hospital de la FACH Santiago, Chile [name] Clínica Colonial Santiago, Chile
Medical Expert:	[name] Cleveland Clinic, OH, USA

^{*}Additional Investigators and Clinical Sites will be listed in a study report or separate document.

Table of Contents

1		NISTRATIVE INFORMATION	
	1.1 1.2	CONTACTS SPONSOR PROTOCOL APPROVAL	
2	ABBF	REVIATIONS / ACRONYMS	11
3	INTR	ODUCTION	12
	3.1	BACKGROUND AND RATIONALE	12
4	SURC	GICAL SYSTEM DEVICE DESCRIPTION	13
5	INDIC	ATION FOR USE AND INTENDED USE	16
6	STUE	Y PURPOSE AND OBJECTIVE	17
7	STUE	Y ENDPOINTS	17
	7.1	SAFETY OUTCOMES	17
	7.2	FEASIBILITY OUTCOMES	17
	7.3	OTHER ASSESSMENTS	17
8	STUD	Y DESIGN	18
	8.1	OVERVIEW	
	8.2	SAMPLE SIZE AND NUMBER OF CENTERS	
	8.3	STUDY DURATION	18
9	STUD	Y PROCEDURES	
	9.1	SUBJECT ELIGIBILITY, PRE-SCREENING, AND EXCLUSION:	
	9.2	SCREENING/BASELINE EVALUATION	
	9.3	PROCEDURE	
	9.4	POST-PROCEDURE / HOSPITAL DISCHARGE	
	9.5	FOLLOW-UP	
	9.6 9.7	UNPLANNED FOLLOW-UP VISITS	
		LOST TO FOLLOW-UP SUBJECTS	
	9.0	STUDY EXIT	
		STUDY SCHEDULE OF ASSESSMENTS	
		1: SCHEDULE OF ASSESSMENTS	
40	DIO	C / DENEET ANAL VOIC	00
10		(/ BENEFIT ANALYSIS BENEFITS	
	10.1 10.2	RISKS	
		MINIMIZATION OF RISK AND MONITORING PROCEDURES	
11	STA	TISTICAL ANALYSIS	24
• •	11.1	STATISTICAL METHODS	
С	P008 Re	vision: A Date: 13Sep2022 CONFIDENTIAL	Page 9 of 41
	_	This document contains proprietary and confidential information of L	

	11.2	SAMPLE SIZE JUSTIFICATION	24
	11.3	SAFETY VARIABLES	24
	11.4	SAFETY	24
	11.5	DEMOGRAPHICS	24
	11.6	HANDLING MISSING DATA	24
	11.7	INTERIM ANALYSIS	
12	DAT	A MANAGEMENT	25
	12.1	DATA COLLECTION	25
	12.2	DATA PROCESSING	25
	12.3	FINAL CLINICAL STUDY REPORT	26
	12.4	PUBLICATION POLICY	26
13	MON	IITORING AND QUALITY CONTROL PROCEDURES	

2 ABBREVIATIONS / ACRONYMS

Abbreviations	Definitions
AE	Adverse Event
CDC	Center for Disease Control and Prevention
CFR	Code of Federal Regulations
CRF	Case Report Form
CRO	Contract Research Organization
EC	Ethics Committee
EUA	Emergency Authorization Use
FDA	Food and Drug Administration
GCP	Good Clinical Practice
GDP	Good Documentation Practice
HHS	United States Department of Health and Human Services
HIPPA	Health Insurance Portability and Accountability Act
ICF	Informed Consent Form
ICH	International Council for Harmonization
IFU	Instructions for Use
IRB	Institutional Review Board
ISO	International Organization for Standardization
LAR	Legal Authorized Representative
LOS	Length of Stay
DRAA	Dual Robotic Arm Accessory
MC	Magnetic Controller
MIS	Minimally Invasive Surgery
MSS	Magnetic Surgical System
N/A	Not Applicable
N/D	Not Done
NSR	Non-significant Risk
OR	Operating Room
PACU	Post Anesthesia Care Unit
PD	Protocol Deviation
PHI	Protected Health Information
PI	Principal Investigator
PP	Per Protocol
RA	Robotic Arm
SADE	Serious Adverse Device Effect
SAE	Serious Adverse Event
SD	Standard Deviation
SDV	Source Document Verification
SOC	Standard of Care
SOP	Standard Operating Procedures
SID	Subject Identification Number
UADE	Unanticipated Adverse Device Effect

CP008 Revision: A Date: 13Sep2022	CONFIDENTIAL	Page 11 of 41

3 INTRODUCTION

3.1 Background and Rationale

Since the introduction of minimally invasive surgery (MIS) in the 1980's, laparoscopy has become the preferred approach for intra-abdominal procedures. With limited access to the surgical field, one of the key requirements of laparoscopic surgery is the ability to achieve and maintain adequate visualization of the surgical target throughout the procedure. During certain MIS procedures, the patient's internal organs can block or obscure the surgical view. A number of surgical instruments (graspers or retractors) have been developed to help mobilize abdominal organs to obtain an adequate surgical view during MIS procedures. Most of these instruments require an additional abdominal wall puncture/incision, leading to potentially increased complications. These complications include risk of postoperative pain, additional scars, injury to major blood vessels and bowel, infection, incision-related hernias, and chronic incisional pain, among others.

To maximize the benefits of MIS, robotic surgery was developed more than 30 years ago. However, the use of the robotic technology has not resulted in demonstrated clinical benefit and the same number of incisions are typically required in robotic procedures (Tan et al; Leal and Campos). Nevertheless, one of the advantages of a robotic platform is that the surgeon has full control of all instruments during the surgery.

One of the goals of MIS is a reduction in the number of abdominal incisions, resulting in less postoperative pain, reducing the risk of incision-related complications, improving the cosmetic results, and increasing overall patient satisfaction after surgery (Nguyen et al). Levita Magnetics developed the Levita® Magnetic Surgical System (MSS) for tissue/organ mobilization. The MSS allows the surgeon to move tissue/organs out of the visual field without requiring a dedicated incision/port for the tool.

Laparoscopic procedures often require several clinical team members to manage the instruments and camera. Ideally only one clinician, who would provide direct control of all the internal surgical tools, would be required. This would both improve the operating environment and reduce the cost of the procedure by decreasing the number of required personnel.

Recently, Levita has developed a Robotic Platform (DRAA) to assist in external management of the controlling magnet which would reduce required personnel and give control of all surgical tools to the same surgeon. The DRAA replaces the commercially available surgical support arm that is currently used with the MSS.

The safety and effectiveness of the MSS has been demonstrated for the retraction of the gallbladder during cholecystectomy (Rivas et al.). This pivotal study, published in the Annals of Surgery and conducted in Chile, supported the marketing clearance of the MSS in the United States in 2016. Initial US experience (Haskins et al.), performed at the Cleveland Clinic, confirmed the results described in the Rivas publication. The MSS has also been used successfully for liver mobilization in bariatric procedures at Duke Regional Medical Center in a series of 40 patients (Davis et al.) As use of the MSS for laparoscopic procedures expands additional data collection is ongoing to detail clinician's experiences with this system in various other laparoscopic procedures.

This current study is intended to evaluate the safety and feasibility of the Dual Robotic Arm Accessory when used with the Magnetic Surgical System for laparoscopic procedures.

4 SURGICAL SYSTEM DEVICE DESCRIPTION

The Dual Robotic Arm Accessory (DRAA) for the MSS, pictured below in **Figure 1**, comprises two collaborative robotic arms, which along with their controllers and control software, are intended for use in medical applications, and additional adaptors, for 1) attaching the Magnetic Controller of the commercially available Levita Magnetics MSS to one robotic arm and 2) attaching a commercially available camera and endoscope to the second robotic arm.

The design of the robotic arms, referred to as the Scope Arm and the Magnet Arm, includes several redundant safety features that make them well suited for use with the MSS in the operating room environment, including hardware and software safety controls.

When mounted on the Scope Arm, an endoscope can be pivoted and translated as controlled by the user, while maintaining minimal motion at the point where the endoscope enters the patient's body via a standard trocar. Similarly, when mounted on the Magnet Arm, the Magnetic Controller can be moved to different positions on or away from the abdominal wall.

[figure not shown]

Figure 1. Diagram of Dual Robotic Arm Accessory: the Magnet RA (on far cart) is holding the Magnetic Controller (MC) of the Magnetic Surgical System; the Scope RA (on near cart) is holding a commercially available endoscope

The MSS is composed of three components: the Detachable Grasper, the Delivery/Retrieval Shaft (together, the "Magnetic Grasper Device"), and an external Magnetic Controller mounted on a Robotic Platform.

The Detachable Grasper and Delivery/Retrieval Shaft make up the Magnetic Grasper Device (**Figure 2**). Once the Magnetic Grasper Device is inserted through an access port and the Grasper is attached to the desired tissue, the Detachable Grasper can be detached from the Delivery/Retrieval Shaft and controlled externally using the Magnetic Controller. Traction of the tissue is maintained through the magnetic field attraction between the Detachable Grasper and the Magnetic Controller. The Magnetic Grasper Device is operated by hand and is inserted into the abdominal cavity through a \geq 10 mm laparoscopic trocar port. The Magnetic Grasper Device is single-use, disposable, and provided sterile to the user.

[figure not shown]

Figure 2. Magnetic Grasper Device

The Magnetic Controller mounted on the robotic arm (Figure 3) emits a magnetic field that attracts the Detachable Grasper. Once the Detachable Grasper is attached to the desired tissue/organ and detached from the Delivery/Retrieval Shaft, the robot arm brings the Magnetic Controller to the external surface of the abdominal wall so that it can magnetically couple to the internal Detachable Grasper under control of the surgeon, the DRAA moves the Magnetic Controller along the surface of the abdomen. When the Magnetic Controller moves, the Detachable Grasper follows, thus retracting the internal tissue/organ to a location of the surgeon's choice. The external Magnetic Controller and the DRAA is reusable, provided non-sterile to the user, and must be placed in an off-the-shelf sterile bag prior to use.

[figure not shown]

Figure 3. Magnetic Controller

The Dual Robotic Arm Accessory (**Figure 4**) includes two robotic arms, control unit(s), and control software. A handheld and/or foot-operated control pad allow

for DRAA control by the surgeon or surgical assistant. One arm of the DRAA attaches the Magnetic Controller using the arm mount of the Magnetic Controller and the second robotic arm attaches a conventional laparoscopic camera.

Figure 4. DRAA. One arm is mobilizing the External Magnetic Controller (external magnet) and the second arm is mobilizing a conventional laparoscopic camera.

The DRAA is certified to international electrical safety and software standards for use in medical products. The design of the DRAA includes several redundant safety features which make it well suited for use with the MSS in the operating room environment. These features include hardware and software safety controls including requirement for an enabling switch, an emergency stop, and controls for the workspace, velocity and axis torque of the robot. As noted, the DRAA is provided non-sterile to the user. While no portions of the DRAA are in direct patient contact, the Robot Arms are in the sterile field. Therefore, prior to use, the Robot Arms must be draped in off the shelf sterile bags (such as the Mayo Stand Cover CFI-708).

5 INDICATION FOR USE AND INTENDED USE

The Magnetic Surgical System is already commercial approved as a class II device, is designed to grasp, hold, retract, mobilize, or manipulate soft tissue and organs in minimally invasive procedures. The Robotic Platform is an accessory designed to facilitate use of the Magnetic Surgical System and an Endoscopic Camera in a hands-free manner.

CP008 Revision: A Date: 13Sep2022	CONFIDENTIAL	Page 16 of 41

The Dual Robotic Arm Accessory (DRAA) is intended to assist in accurate control of the Magnetic Surgical System and a commercially available endoscope. It is intended for use by trained and qualified surgeons, who are familiar with this device prior to surgery, in an operating room environment in accordance with the representative specific procedures set forth in the Instructions for Use.

6 STUDY PURPOSE AND OBJECTIVE

The purpose of this study is to evaluate the safety and feasibility of the Robotic Platform used with the Levita Magnetic Surgical System in laparoscopic procedures.

7 STUDY ENDPOINTS

The following endpoints will be evaluated in all subjects who undergo laparoscopic procedures using the Robotic Platform and Magnetic Surgical System.

7.1 Safety Outcomes

All adverse events will be captured and reported. Adverse events will be summarized by relatedness to the device and/or procedure, seriousness and level of severity. If device related, AEs will be further characterized as to relationship to the MSS the DRAA or both.

7.2 Feasibility Outcomes

Ability to utilize the Levita MSS with the DRAA as intended in laparoscopic procedures. The following outcomes will be considered in this feasibility study:

- The DRAA is able to engage, move, and decouple with the MSS as intended / controlled by the surgeon
- The DRAA is able to provide adequate endoscopic visualization via a conventional endoscopic system as intended / controlled by the surgeon
- The procedure is successfully performed with the MSS and DRAA.
- The MSS or the DRAA cannot be successfully used and due to a MSS or DRAA performance issue the procedure must be converted to an open procedure.

7.3 Other Assessments

- Operative time
- Time spent in the Post Anesthesia Care Unit (PACU)
- Length of stay (LOS) (time from admittance to post-anesthesia care unit until hospital discharge)

CP008 Revision: A Date: 13Sep2022	CONFIDENTIAL	Page 17 of 41

- Conversion rate (conversion to an open procedure due to inadequate MSS performance)
- Number of required surgeons
- Estimated blood loss
- MSS and Robotic Platform malfunctions
- Patient and Surgeon satisfaction with the system

8 STUDY DESIGN

8.1 Overview

This feasibility study is a prospective, multi-center, single-arm, open label study designed to assess the safety and feasibility of the use of the Dual Robotic Arm Accessory with the Levita Magnetic Surgical System in laparoscopic procedures.

8.2 Sample Size and Number of Centers

The study will be conducted at up to three (3) clinical sites with a target maximum of 50 subjects in which the Robotic Platform and Levita Magnetic Surgical System is used for laparoscopic procedures.

8.3 Study Duration

Enrollment of subjects in this study is anticipated to take up to 12 months. Clinical follow-up evaluations will be conducted at discharge, 7 days, and 30 days following surgery. The total study duration is expected to be approximately 13 months.

9 STUDY PROCEDURES

9.1 Subject Eligibility, Pre-Screening, and Exclusions

All individuals presenting for elective laparoscopic procedures are potential candidates and will be screened for eligibility. Study clinicians will select subjects based on knowledge/experience. A Screening/Enrollment Log will be provided to the study sites to maintain a cumulative tracking of all screened subjects.

Subjects must meet all study entrance criteria for enrollment in the clinical study. Reasons for screening failure(s) will be documented.

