9.1.2 Exclusion Criteria

Individuals must be EXCLUDED from participation in this study if ANY of the following exclusion criteria are met:

- 1. Individuals with pacemakers, defibrillators, or other electromedical implants
- 2. Individuals with ferromagnetic implants
- 3. Individuals with significant comorbidities: cardiovascular, neuromuscular, chronic obstructive pulmonary disease, and urological disease (renal failure)
- 4. Individuals with clinical history of impaired coagulation confirmed by abnormal blood tests
- 5. Anatomical abnormality or disease of intended target tissue noted after initiation of index procedure that would prevent device use
- 6. The individual is pregnant or wishes to become pregnant during the length of study participation
- 7. Individual is not likely to comply with the follow-up evaluation schedule
- 8. Is participating in a clinical trial of another investigational drug or device
- 9. Is a prisoner or under incarceration

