9.2 Screening/Baseline Evaluation

Patients will be prescreened for eligibility and if qualified will be approached with the study information and asked if they are willing to participate. The Screening visit will occur within 30 days prior to the laparoscopic procedure.

Informed consent will be obtained per Section 13.3. All patients who sign a consent form are considered study subjects. A study participant is considered enrolled after they have signed an informed consent form and after the inclusion/exclusion criteria have been met.

The following evaluations are required at the time of subject screening /baseline:

- Demographic Information: gender, race, age, weight, and height, and smoking status
- Medical / Surgical History
- Pre-operative blood draw for determination of coagulation disorders if warranted
- Urine pregnancy test for women of childbearing potential. Note that if the screening test is more than 1 week prior to the index

procedure, a second urine pregnancy test is required within 7 days of the index procedure.

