10.3 Minimization of Risk and Monitoring Procedures

Levita Magnetics has attempted to mitigate risks as much as possible through product design and development of the MSS which included *in vivo* performance testing, human factors testing, non-clinical performance testing, clinical testing of the MSS in other surgical procedures, biocompatibility testing, sterilization validation, reprocessing validation and shelf-life validation. Additionally, careful labeling, IFU and training are provided as detailed below for the MSS and DRAA.

Risks will be further mitigated through selection of qualified physicians with competence in minimally invasive surgery, appropriate training, and study monitoring.

CP008 Revision: A Date: 13Sep2022	CONFIDENTIAL	Page 22 of 41

Investigators who participate in the study will be experienced and skilled in laparoscopic surgical techniques. Additionally, Investigators, in conjunction with the investigational site, will have adequate resources for participation in a clinical study.

The study has been designed to ensure treatment and follow-up of subjects are consistent with current medical practice.

Each Investigator will ensure oversight and approval of the study by the Ethics Committee (EC) prior to initiation of the clinical study at his/her investigational site.

The Investigator and study personnel will be trained on the clinical protocol. All Investigators who have not previously used the Levita MSS will undergo training with MSS prior to first use during the clinical study.

All Investigators and operating room support personnel will be provided with a detailed IFU during training and as a reference for review as needed.

The IFU details appropriate safety zones for use of the Magnetic Controller in an OR setting and considerations for users of a product with a strong magnet.

Study personnel are also trained with and receive a "Magnetic Surgery Screening Checklist" and Operating Room (OR) signage to ensure safe use of the system for subjects and users.

Subjects will be carefully evaluated against the inclusion/exclusion criteria prior to entering the clinical study to ensure that their diagnosis and medical status are appropriate for participation in the clinical study.

Subjects will be monitored up to the 30-day follow-up visit as defined in the study protocol. The follow-up visit will be with an Investigator to monitor the subjects' status.

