15.11 Criteria for Suspending/Terminating an Investigational Site

Levita Magnetics reserves the right to stop the enrollment of subjects or terminate an investigational site at any time after the study initiation visit for any of the following reasons:

- Failure to obtain written Informed Consent.
- Failure to report SAE or USADE to Levita Magnetics within 24 hours of knowledge.

CP008 Revision: A Date: 13Sep2022	CONFIDENTIAL	Page 37 of 41

- Repeated failure to complete Case Report Forms (CRFs) Loss of (or unaccounted for) investigational product inventory.
- Repeated protocol violations
- Failure of Investigator to comply with training or Instructions for Use
- Failure to screen at least 1 patient and within any 2-week period
- Persistent non-compliance with the protocol
- Persistent non-compliance with EC or regulatory requirements

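### Does Section 9.1 allow an undocumented choice among eligible patients, and is the spread of cases behind n = 50 left unshown?

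*Combined protocol and SAP*

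**What the plan says.** Section 9.1 opens by making everyone who presents for elective laparoscopy a potential candidate to be screened. It then states: "Study clinicians will select subjects based on knowledge/experience". It provides a log that tracks all screened subjects, requires every entrance criterion to be met, and adds "Reasons for screening failure(s) will be documented".

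Two other sections describe entry. Section 9.2: "Patients will be prescreened for eligibility and if qualified will be approached with the study information and asked if they are willing to participate". Section 10.3: "Subjects will be carefully evaluated against the inclusion/exclusion criteria prior to entering the clinical study".

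Exclusion 5 in Section 9.1.2 can arise during surgery: "Anatomical abnormality or disease of intended target tissue noted after initiation of index procedure that would prevent device use".

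On numbers, Section 8.2 has up to three sites "with a target maximum of 50 subjects", counted as subjects in whom the system is used; the synopsis words the same 50 as enrolled, competitively. Section 11.2 explains the 50 by use across several surgeons and types of operation. The intra-operative list in Section 9.3 includes the number of surgeons required, general device and procedure observations, and a video of the operation. It does not name procedure type or operating surgeon. Section 11.1 declares the study non-inferential and allows descriptive tables of baseline characteristics and outcomes.

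**The concern.** With no control arm, the observed feasibility and adverse event proportions are the result, and Section 12.4 foresees possible use in a regulatory submission. If clinicians may choose among eligible patients, those proportions describe chosen cases. The baseline tables would not reveal this, because they cover only subjects in the study. Reasons are required for screening failures, a term the protocol does not define, so an eligible patient who was passed over might be logged without one. Such reasons are hard to reconstruct later.

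The second strand is that the only concrete rationale for 50 subjects is breadth of surgeons and operations, and nothing commits the report to showing that breadth. Operative time, blood loss and length of stay pooled over unnamed operations would be hard to read.

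**Working it through.** **1. What the selection sentence means.** Set side by side, Section 9.1 screens all comers, Section 9.2 approaches those who qualify, and Section 10.3 evaluates subjects against the criteria. Two exclusions cannot be applied without judgement: whether a comorbidity is significant (exclusion 3) and whether the person is likely to attend follow-up (exclusion 7). Knowledge and experience are what those criteria call on. This reading makes the three sections agree. The reading as free choice among eligible patients puts 9.1 in conflict with 9.2.

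**2. Who could be lost without a reason.**

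| Group | Covered by |
|---|---|
| Fails a criterion | Log, with reason (9.1) |
| Declines consent | Fails inclusion 3, so log with reason |
| Eligible, not approached | Should not arise under 9.2; if it does, in the log as screened, reason not clearly required |
| Enrolled, device use prevented (exclusion 5) | CRF for every enrolled subject (12.1); Section 7 ties the endpoints to subjects operated on with the system |

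Only the third row is open, and only on the less likely reading.

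**3. Can the documents size the open group?** The one screening figure is a ground on which the sponsor may stop a site, in Section 15.11: "Failure to screen at least 1 patient and within any 2-week period". Section 8.3 gives the period: "Enrollment of subjects in this study is anticipated to take up to 12 months". Take 12 months as 52 weeks, or 26 two-week periods, and use the synopsis wording of at most 50 enrolled:

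- Three sites at the floor: 3 × 26 = 78 screened; 78 − 50 = 28 not enrolled; 28/78 = 35.9%.
- Two sites: 2 × 26 = 52; 52 − 50 = 2; 2/52 = 3.8%.
- One site: 26, which is below 50, so possibly 0.
- Three sites reach 50 screened after 50/1.5 = 33.3 weeks; if screening stops then, possibly 0.
- Assumed rate of one patient per site per week, three sites: 156; 156 − 50 = 106; 106/156 = 67.9%.

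These are minimum counts of patients not enrolled for any reason. They run from 0% to 68%, and the part due to clinician choice could be none or all of them. The floor is also a discretionary stopping ground, not an expected rate. The arithmetic is right but says nothing about selection.

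**4. Precision.** The plan gives no alpha, power, target rate or interval width, so 50 has no formula to reproduce. For scale, the exact two-sided 95% upper limit with zero events is 1 − 0.025^(1/n): 7.1% at n = 50 and 11.6% at an assumed n = 30. These limits treat the sample as given and carry no information on how it was chosen. The same formula gives 31% at n = 10 and 52% at n = 5 (assumed stratum sizes), so rates by procedure type may mean little.

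**5. Is the spread of cases lost?** The operation is scheduled before entry (inclusion 2), recorded on video (9.3) and held in source documents that sites must keep (15.13). Device records carry date of use and subject number (13.3). Procedure type and operator should be recoverable from these, and the CRF, which is not in the documents, may hold them already. Section 11.2 states why 50 was chosen; it does not promise a display.

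**The case for a change.** The best argument for a change is that Section 9.1 separately requires all entrance criteria to be met. If selecting meant only applying them, the selection sentence would be redundant, so a discretionary reading is natural. No section requires consecutive enrolment, enrolment is competitive without a minimum or cap per site or surgeon, and up to three sites could read the sentence differently.

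Selection can also matter in principle. Assume that 20% of eligible patients carry a 15% event risk and 80% carry 2.5%. The overall rate is 0.2 × 0.15 + 0.8 × 0.025 = 5%. Taking only the lower-risk patients halves it to 2.5%, and the chance of seeing at least one event in 50 falls from 1 − 0.95^50 = 92% to 1 − 0.975^50 = 72%.

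What stands is that the sentence is loose and the protocol does not expressly commit to a patient-flow count or a case count by surgeon and operation. The rest carries less weight. The risk split is wholly assumed. Extra logging would leave clinicians the same discretion, so the sample and its rates would not change; a reason column would only make any choice visible. Section 13.2 has site staff trained on the protocol before enrolment, which is an ordinary occasion to settle one meaning. Confidence intervals would answer neither complaint, since they do not reflect selection.

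**Conclusion.** No change to the plan is needed. The wording tension between Sections 9.1 and 9.2 is real but minor, and the more coherent reading removes it. The missing detail on patient flow and case mix is the kind that analysts of a feasibility study of at most 50 cases ordinarily supply in the report that Section 12.3 requires, within the descriptive tables that Section 11.1 already allows. No test, threshold or sample size calculation is affected, because the plan has none. Any effect is on interpretation and generalisability, and its size cannot be estimated from the documents.

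This rests on three assumptions: that sites approach qualified patients as Section 9.2 says, that a refusal is logged as failing inclusion 3, and that operator and procedure type can be read from the surgical records. If sites did choose freely among eligible patients, the reasons for passing patients over would be of interest to the reader, but the planned analysis would be the same.
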